### 5.3. Graphical Testing Scheme

To control type I error, a graphical testing scheme (Bretz et al. 2011) presented in [Figure GBGE.5.1](#) will be used to compare treatments regarding selected secondary objectives once the primary objective has been achieved. In [Figure GBGE.5.1](#) the numbers in the circles indicate the fraction of alpha used for the first hypothesis tests. The numbers along the arrows represent the fraction of alpha from a hypothesis, if it is rejected, to allocate to the next hypothesis.

The graphical testing scheme will be performed for the efficacy estimand and the treatment regimen estimand (see [Section 5.1](#)) separately.

**Figure GBGE.5.1. Graphical testing scheme for Study H9X-MC-GBGE.**

H1: Primary objective, superiority test of dulaglutide 1.5 mg versus placebo on hemoglobin A1c (HbA1c) change from baseline at 24 weeks.

H2: Primary objective, superiority test of dulaglutide 0.75 mg versus placebo on HbA1c change from baseline at 24 weeks.

H3: Superiority test of dulaglutide 1.5 mg versus placebo on HbA1c target 7.0% at 24 weeks.

H4: Superiority test of dulaglutide 0.75 mg versus placebo on HbA1c target 7.0% at 24 weeks.

H5: Superiority test of dulaglutide 1.5 mg versus placebo on body weight change from baseline at 24 weeks.

H6: Superiority test of dulaglutide 0.75 mg versus placebo on body weight change from baseline at 24 weeks.

H7: Superiority test of dulaglutide 1.5 mg versus placebo on FBG change from baseline at 24 weeks.

H8: Superiority test of dulaglutide 0.75 mg versus placebo on FBG change from baseline at 24 weeks.

## 5.4. Patient Population

The following patient populations described in [Table GBGE.5.1](#) will be used to analyze the data. The data collected in this study will be presented as listings by investigator site, patient, and treatment.

**Table GBGE.5.1. Analysis Populations**

Population	Definition
All Entered	All patients who signed informed consent forms (ICF)
All Randomized	All patients who were randomized to a treatment arm
Non-randomized	All patients who entered, but not randomized, to a treatment arm
Intent-to-treat (ITT)	All randomized patients who have taken at least one dose of the study medication
Per-protocol (PP)	All patients in ITT and who also meet the following criteria: 
 
• Have no important protocol deviations (Section 5.7)
 
• Completed the treatment phase (24 week [Visit 11]) for primary end point (ie, did not discontinue from the study early)
 
• Are at least 75% compliant with study drug for at least 75% of the visits
 

Completer Population	The completers population will be defined as those who: 
 
• Completed the treatment period (ie, did not discontinue early from the study)
 

The complete list of protocol deviations leading to exclusion from the PP population is provided in Section 5.7.

## 5.5. Patient Disposition

A listing of patient discontinuation will be presented for all randomized patients. Frequency counts and percentages of all patients entered, randomized/enrolled, completing and discontinuing from the study and study treatment will be presented for all treatment groups. A summary of discontinuations will also be presented by visit. The overall percent discontinued comparisons among the treatments will be performed using a Chi-square test or Fisher's exact test.

## 5.6. Patient Characteristics

Demographic and baseline characteristics will be summarized by treatment group for ITT, PP and completer populations. For continuous measures, summary statistics will include sample size (n), mean, median, min, max, and SD. Treatment differences will be analyzed using analysis of variance (ANOVA) model with treatment as the factor. For categorical measures, summary statistics will include sample size, frequency and percent. Treatment difference will be compared using Fisher's exact test or Chi-square test.

## 5.7. Protocol Deviations

Important protocol deviations will be listed for all randomized patients. The rationale for choosing the important protocol deviations was based on their potential to impact the primary analysis. The following protocol deviations will be considered important and patients with these protocol deviations will be excluded from the PP population:

- Patients violating the following Inclusion/Exclusion criteria:

- Have HbA1c <7.0% or >9.5% at study entry (Visit 1) or at Visit 2 for patients without stabilization; HbA1c <7.0% or >9.5% at study entry (Visit 1) or at Visit 4 for patients with stabilization;
- Patients with Type 1 diabetes
- Have any hematologic condition that may interfere with HbA1c measurement (for example, hemolytic anemia, sickle-cell disease)
- Use of weight loss drugs within 3 months prior to study entry or use of systemic glucocorticoids 1 month prior to study entry, or use of these medications between study entry and Visit 5;
- Use of ANY other oral antihyperglycemic medications (OAMs) (other than sodium-glucose cotransporter 2 [SGLT2] inhibitors and metformin), GLP-1 receptor agonist (RA), pramlintide or insulin 3 months prior to study entry, or between study entry and Visit 5; or initiation of metformin between study entry and Visit 5; short-term use of insulin for acute care ( $\leq 14$  days) during the 3-month period prior to entry is not protocol deviation;
- Missing HbA1c at baseline (Visit 5) or at 24 weeks (Visit 11)
- Patients who do not have an overall compliance with study drug at least 75% for at least 75% of the visits during the study
- Patients who took medications that were prohibited per protocol for >14 days (cumulative) after randomization (Visit 5-Visit 11), including:
  - Excluded antihyperglycemia medications; including insulin use for acute care; Note: use of rescue therapy medications is not considered protocol deviation;
  - Other protocol-prohibited medications (systemic glucocorticoids or weight loss medications);
- Informed consent was never obtained
- Patients who are randomized but the informed consent data is missing.

## 5.8. Concomitant Medications

Glucose lowering agents will be summarized by treatment at entry, baseline (Visit 5), and for the entire 24-week treatment period. Doses of SGLT2 inhibitors and metformin will be summarized at baseline (Visit 5) and at study end (Visit 11). Other pre-specified concomitant medications of interest (antihypertensives, lipid lowering agents, antithrombotic agents, anti-inflammatory agents, and cardiac therapy) will be summarized by treatment at baseline (Visit 5).

Antihypertensive medications will be additionally summarized for the entire 24-week treatment period by treatment group including frequency and reasons for dose change. Frequency of use of non-study glucose-lowering medications will be summarized at baseline (Visit 5) and for the entire 24-week treatment period by treatment group.

## 5.9. Study Drug Compliance

Study drug compliance for each visit is defined as taking at least 75% of the scheduled injections of the study drug for the period preceding that visit. Overall treatment compliance for each patient is defined as taking at least 75% of the injectable study drug for at least 75% of the visits, that is, the overall compliance percentage is at least 75% for this patient. The overall compliance in percentage for each patient will be calculated by taking the number of visits the patient was compliant divided by the total number of visits with non-missing compliance data for this patient \*100. Study drug compliance will be listed and summarized using ITT population. The compliance will be summarized and presented in descriptive statistics that include the sample size (n), mean, SD, median, min, and max. The frequency and percent of patients who are compliant will be compared between the treatment groups using Chi-square test or Fisher's exact test at each visit and overall.

## 5.10. Treatment Exposure

Treatment exposure is defined as the time from when the patient is randomized at Visit 5 and receives study drug until the patient either discontinues from treatment or completes the treatment period as planned.

The duration of treatment exposure will be listed and summarized by treatment group for ITT, PP, and completer populations. Duration of exposure will be categorized into the following groups:  $\leq 14$  days,  $>14$  to  $\leq 28$  days,  $>28$  to  $\leq 56$  days,  $>56$  to  $\leq 84$  days,  $>84$  to  $\leq 126$  days,  $>126$  to  $\leq 168$  days and  $>168$  days. These categories will be summarized as frequency by treatment group. Summary statistics will include mean per patient exposure in days, SD, median, min, and max. The duration of treatment exposure will be analyzed using one-way ANOVA with treatment as fixed effect.

## 5.11. Primary Efficacy Analysis

The primary outcome is the difference in HbA1c mean change from baseline to 24 weeks in the ITT population. The primary hypothesis of interest in this placebo-controlled study is whether dulaglutide has superior efficacy compared to placebo, in patients already treated with SGLT2 inhibitors.

The primary analysis model will be an MMRM for HbA1c change from baseline to 24 weeks in the ITT population (Visit 11) with treatment, country, SGLT2 inhibitor dose ("low" versus "high"), metformin use ("yes" versus "no"), visit and treatment-by-visit as fixed effects, baseline HbA1c as a covariate, and patient as a random effect.

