### 3. Revision History

The protocol for this study was approved on 29-Jul-2015. Protocol amendment (a) was approved on 21-Aug-2015. Version 1 of this Statistical Analysis Plan (SAP) was approved prior to first patient visit (FPV). Version 2 of the SAP was developed based on the request from FDA that the ITT estimand (treatment regimen estimand, including the post-rescuedata) be used for the primary analysis. This revision was approved before the last patient visit. The following changes were made in this revision: 1) sample size due to protocol amendment; 2) the definition of the completers population for consistency with other dulaglutide studies; 3) hypoglycemia rate analysis using linear mixed model instead of GEE for better control of the type I error rate; 4) including baseline HbA1c-by-visit interaction term in the HbA1c target analysis to improve model convergence.

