## 5. A Priori Statistical Methods

### 5.1. Determination of Sample Size

With 120 completers per arm, the study will have 90% power for demonstrating superiority of either dulaglutide 1.5 mg or 0.75 mg versus placebo in change from baseline in mean hemoglobin A1c (HbA1c) at 24 weeks, assuming a standard deviation (SD) of 1.2%, a difference between dulaglutide and placebo of 0.55%, and a 2-sided significance level of 0.025. Assuming that the dropout rate is 15% for the entire study period, the study will need to enroll at least approximately 142 patients in each arm for a total of 426 patients enrolled. Assuming a screen fail rate of 40%, a total of approximately 710 patients will be screened to meet these enrollment number requirements.

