The baseline will be Visit 5, except for HbA1c. Patients who do not need stabilization will have blood drawn for baseline HbA1c at Visit 2, and those who need stabilization at Visit 4. For all variables except HbA1c, if baseline data are missing, the last nonmissing measurement taken prior to Visit 5 will be used for the baseline measurement. For HbA1c, if baseline data are missing, the imputation will be conducted only if an additional value between Visit 2 and randomization (patients not needing stabilization) or Visit 4 and randomization (patients needing stabilization) is collected. The endpoint for the primary analysis is defined as the change from baseline in HbA1c at 24 weeks (Visit 11). Key secondary endpoints are percent to goal in HbA1c (<7.0%) at 24 weeks and change from baseline in FBG (central laboratory) and body weight at 24 weeks.

Two analysis models will be used for the primary and key secondary continuous efficacy measures. The primary analysis will be mixed-model repeated measure (MMRM) analysis using restricted maximum likelihood (REML). An unstructured covariance structure will be used to model the within-patient errors. If this model fails to converge, the following covariance structures will be tested in order:

- Toeplitz with heterogeneity
- autoregressive with heterogeneity, by visit
- compound symmetry with heterogeneous variances by visit,
- Toeplitz
- autoregressive
- compound symmetry without heterogeneous variances, by visit

The first covariance structure that converges will be used.

The secondary analysis for the primary and key secondary continuous endpoints will be analysis of covariance (ANCOVA). Missing endpoints will be imputed with the last (postbaseline) observation carried forward (LOCF). The percentage of patients achieving the target HbA1c of <7.0% at 24 weeks will be analyzed using a longitudinal logistic regression with repeated measurements.

A graphical testing approach will be used to strongly control for type 1 error to test for superiority of each of the dulaglutide doses versus placebo at 24 weeks for the following

measures: (1) change from baseline in HbA1c, (2) change from baseline in FBG (central laboratory), (3) percent achieving HbA1c <7.0%, and (4) change from baseline in body weight.

[figure not shown]

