### **5.12.3. Percentage of Patients Achieving a Target HbA1c <7.0%**

For percentages of patients achieving target HbA1c of <7.0 at 24 weeks, longitudinal logistic regression with repeated measurements (generalized linear mixed models, Liu and Zhan 2011) will be used. The model will include independent variables for treatment, country, SGLT2 inhibitor dose (“low” versus “high”), metformin use (“yes” versus “no”), visit, baseline HbA1c - by-visit interaction, and the treatment-by-visit interaction as fixed effects, and baseline HbA1c as a covariate. These analyses will be performed with post-rescue data excluded (considered missing), and separately with all post-rescue data included. In addition, an analysis of percentage of patients on HbA1c targets will be performed where patients who have been rescued or have no post-baseline data will be considered (imputed) as not having achieved the target.

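### The primary MMRM fixes one baseline HbA1c slope for all visits; if the true slopes differ by visit, Week 24 loses a little precision and may tilt slightly towards dulaglutide, and one added term removes both

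*SAP*

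**What the plan says.** SAP section 5.11 lists the primary model's terms: treatment, country, SGLT2 inhibitor dose, metformin use, and then "visit and treatment-by-visit as fixed effects, baseline HbA1c as a covariate, and patient as a random effect". Baseline HbA1c appears once. No other section adds a baseline-by-visit term to this model.

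Section 5.2 leaves the covariance among post-baseline visits free: "An unstructured covariance structure will be used to model the within-patient errors". It lists simpler structures only as fallbacks.

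The model for HbA1c below 7.0% in section 5.12.3 does let the baseline effect vary over time; its terms include baseline HbA1c "by-visit interaction, and the treatment-by-visit interaction as fixed effects, and baseline HbA1c as a covariate". Section 5.13.2 does the same for the 6.5% target. Section 3 gives the reason: "including baseline HbA1c-by-visit interaction term in the HbA1c target analysis to improve model convergence".

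Section 5.11.1 repeats the primary MMRM in the per-protocol and completer populations, analyses the placebo-imputed (pMI) data with it, and reads the tipping point from it.

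**The concern.** In a model for change from baseline, the baseline slope at a visit is the regression of that visit's value on baseline, minus 1. If baseline predicts later values less well than earlier ones, the slope grows more negative over time. A common slope then misfits Week 24, for two possible losses.

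- **Precision.** Baseline variation left unexplained at Week 24 goes into the residual.
- **Bias.** With complete data, randomisation balances baseline and the misfit cancels between arms. It need not cancel if the patients missing at Week 24 differ in baseline between arms. If placebo patients with high baseline are missing more often, a slope that is too shallow understates their expected fall, and the difference moves towards dulaglutide.

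The efficacy estimand in section 5.2 drops post-rescue data, which is one route to such missingness. The SAP's own time-to-rescue model (section 5.15.2.2) contains both treatment and baseline HbA1c, so dependence on both is plausible, though the SAP does not state it. The pMI and tipping-point analyses reuse the model and would not reveal the restriction. The LOCF ANCOVA has its own endpoint slope but also changes the handling of missing data, so a difference there could not be attributed to the slope.

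**Working it through.** **1. The plan's own figure.** Section 5.1 states: "With 120 completers per arm, the study will have 90% power", "assuming a standard deviation (SD) of 1.2%, a difference between dulaglutide and placebo of 0.55%, and a 2-sided significance level of 0.025".

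- n per arm = 2 × (2.2414 + 1.2816)² × 1.2² / 0.55² = 2 × 12.41 × 4.760 = 118.2, so 119 (stated 120).
- Power at 120 = Φ(0.55 / (1.2 × √(2/120)) − 2.2414) = Φ(3.550 − 2.241) = 0.905.
- "Assuming that the dropout rate is 15% for the entire study period": 120 / 0.85 = 141.2, so 142 per arm, and 3 × 142 = 426.

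The sample size reproduces.

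**2. Inputs the SAP does not give, so assumed.** Four post-baseline HbA1c visits; baseline SD 0.65 (guided by the 7.0% to 9.5% range in section 5.7); serial correlation 0.8; raw SD of change at Week 24 of 1.2; about 15% missing per arm. Four slope profiles were tried, each the same in all arms.

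**3. Common slope against by-visit slopes on the same simulated data, unstructured covariance.** Standard errors come from very large samples rescaled to 142 per arm, with dropout completely at random. The shift is the common-slope estimate minus the by-visit estimate when placebo missingness rises with baseline and dulaglutide missingness is flat; negative favours dulaglutide. The last column repeats the shift in 300 trials of 142 per arm (Monte Carlo error at most 0.003).

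| Slope, first to last visit | SE common | SE by visit | Ratio | Shift | Shift, 142 per arm |
|---|---|---|---|---|---|
| Equal, −0.50 throughout | 0.1436 | 0.1436 | 1.000 | 0.000 | 0.000 |
| Mild, −0.30 to −0.50 | 0.1448 | 0.1437 | 1.008 | −0.008 | −0.009 |
| Moderate, −0.20 to −0.55 | 0.1455 | 0.1424 | 1.021 | −0.016 | −0.018 |
| Strong, −0.10 to −0.70 | 0.1464 | 0.1380 | 1.061 | −0.031 | −0.031 |

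In the moderate case the fitted common slope was about −0.18 against −0.55 at Week 24: with high correlation the fit follows the early visits.

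**4. Variations.**
- Correlation 0.5 or 0.65, moderate slopes: ratio 1.010 or 1.013, shift −0.018 or −0.019.
- Slopes −0.4 to −0.5 in all arms: standard error wider by 0.15%.
- Placebo slope flat at −0.35 and only the dulaglutide slopes growing (−0.25 to −0.50, or −0.20 to −0.60): wider by 0.4% or 1.0%.
- Three visits instead of four: slopes −0.15, −0.35, −0.50 give 1/0.982 = 1.018 and a shift of −0.013; slopes −0.1, −0.4, −0.7 give about 1/0.95 = 1.05 and −0.021.
- Opposite baseline dependence in the two arms, an extreme case: −0.017, −0.032 and −0.057 for mild, moderate and strong.
- Data complete or missing completely at random: shift about 0.001 or less in the large samples.

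**5. Consequence for the test.** With a standard error of about 0.145, the shifts in the table are 0.0084/0.145 = 0.06, 0.0161/0.145 = 0.11 and 0.0314/0.145 = 0.22 standard errors. By normal approximation a two-sided 0.05 test then runs at 0.050, 0.051 and 0.055 (0.068 at the extreme shift of 0.057).

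**6. Consequence for power.** If 1.2 is the raw SD of change, the unadjusted standard error at 142 per arm is 1.2 × √(2/142) = 0.1424. The complete-data common-slope model gives 0.137 to 0.140, which is still smaller. If 1.2 is instead read as the model's residual SD, power at 120 per arm goes from 0.905 to 0.900 (mild), 0.892 (moderate) or 0.866 (strong).

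**The case against.** The strongest reply is that the model is fully specified, that nothing in it is stated wrongly, and that a common slope is a legitimate choice. The SAP gives no slopes by visit, so slope change cannot be taken as fact. Baseline HbA1c is drawn at Visit 2 or Visit 4, before randomisation at Visit 5 (section 5.2), so regression to the mean may already be present at the first post-baseline visit and part of the slope may be flat. The 15% in section 5.1 is dropout, not rescue; no rescue rate or pattern is given. The treatment-regimen estimand keeps post-rescue data, so the rescue route does not reach it. All of this stands, and it is why the point is conditional and its range starts at zero.

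A reader might go further in three ways that the SAP does not support.

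- **That the SAP contradicts itself** by including the interaction in the target models but not here. Section 3 says the term was added there for convergence, a matter for the logistic mixed model, so the two choices can coexist.
- **That the trial is underpowered or the primary result unsafe.** Steps 5 and 6 show otherwise in realistic cases.
- **That the body weight and SMPG models suffer equally.** They share the structure, but neither was computed, so no claim is made about them.

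What the reply does not supply is a benefit from the restriction: with equal slopes the fuller model costs almost nothing.

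**Conclusion.** The point holds in conditional form, as an optional improvement. If baseline slopes differ between visits, the common-slope model widens the Week 24 standard error by about 0% to 2% in mild to moderate scenarios, and by 5% to 6% only with steep slope change. If missingness also depends on arm and baseline, the estimate shifts by about 0.01 to 0.03 HbA1c points towards dulaglutide, roughly 2% to 6% of the assumed 0.55. With equal slopes neither effect exists.

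These sizes rest on assumed slopes, visits, correlation and missingness, so they are a range and not an estimate for this trial. The case for acting is that the restriction sits in the primary model used for both primary estimands, its possible bias runs in the favourable direction, and the planned sensitivity analyses would not isolate it.

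**What to change.** In section 5.11, add baseline HbA1c-by-visit to the fixed effects of the primary HbA1c MMRM. In section 5.11.1, state that the pMI and tipping-point imputation and analysis models carry the same term.

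The cost is a few words and one degree of freedom per extra visit, with 426 patients planned. In the simulations this cost at most about 0.3% in standard error when slopes were equal, and it removed the shift when they were not. The sample size needs no change.

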### 5.11.1. Additional Analyses for Primary Endpoint

The primary analysis model, MMRM, will be repeated for the PP population and the completer population as sensitivity analyses. If the conclusion differs from the analysis of the ITT population, the data and analyses will be further investigated.

The secondary analysis model will be an ANCOVA (only for excluding rescue data) for HbA1c change from baseline to 24 weeks (Visit 11), using a similar model as described above with

treatment, country, SGLT2 inhibitor dose (“low” versus “high”), and metformin use (“yes” versus “no”) as factors and baseline HbA1c as a covariate. Missing endpoints will be imputed with the LOCF using postbaseline data only using ITT population.

To investigate departure from the Missing At Random (MAR) assumption for the primary analysis for both efficacy and treatment regimen estimands, a sensitivity analysis using a particular missing not at random (MNAR) assumption will be performed. Specifically, a placebo multiple imputation (pMI) will be performed (Ayele et al. 2014), which assumes that the drug effect in missing data and post-rescue data in both the placebo arm and dulaglutide arm was like the observed effect in the placebo arm (excluding post-rescue data). This is essentially the “copy reference” approach as described in Carpenter et al. 2013. This approach is in essence assuming that the drug effect will decay over time, in accordance with the correlation structure implied by the data. Data imputed this way will be analyzed with the same MMRM model as the primary analysis. This particular MNAR assumption can be viewed as a “worst reasonable case” assessment of the two estimands..

For both the efficacy estimand and the treatment regimen estimand, a tipping point analysis will be performed in which the missing data are imputed with a MAR assumption. However, prior to analysis, in the dulaglutide arm the imputed values will be replaced by the imputed value plus delta. Multiple values of delta will be tried until the value at which the conclusion from the MMRM analysis changes.

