There will be 2 primary estimands to compare the placebo and the dulaglutide arms in terms of the primary measure of HbA1c change from baseline to 24 weeks. One primary estimand will be an efficacy estimand which will not use post-rescue data; the other primary estimand, requested by the US Food and Drug Administration (FDA), will be an ITT estimand (treatment regimen estimand) which will use post-rescue data. The efficacy estimand compares the benefit of the initially randomized treatments assuming all patients remained in the study and did not take additional or alternative antihyperglycemic medication. The estimate of mean change from baseline to endpoint reflects what would have been observed if patients stayed on their initially randomized treatments. The treatment-regimen estimand compares the benefit of treatment regimens as they are actually taken. The estimate of mean change from baseline to endpoint reflects what was actually observed regardless of use of any additional or alternative antihyperglycemic agents. Both estimands will use the same primary analysis model, and each will be tested at the full significance level of 0.05.

Analyses of the key secondary efficacy outcomes (percent to goal in HbA1c, FBG, body weight) and hypoglycemia will be performed on the full dataset with and without censoring data collected after rescue medication for any reason.

Unless otherwise noted, all tests of treatment effects will be conducted at a 2-sided alpha level of 0.05, and confidence intervals (CIs) will be calculated at 95%, 2-sided. All tests of interactions between treatment groups and other factors will be conducted at a 2-sided alpha level of 0.10.

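### The placebo multiple imputation replaces observed post-rescue data, so it does not fit the treatment-regimen estimand and may not be its worst reasonable case

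*SAP*

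**What the plan says.** Section 5.2 sets two primary estimands for HbA1c change at 24 weeks. The efficacy estimand leaves post-rescue data out. The other "will be an ITT estimand (treatment regimen estimand) which will use post-rescue data", and its estimate "reflects what was actually observed regardless of use of any additional or alternative antihyperglycemic agents". Section 3 records that Version 2 of the SAP was written because the regulator asked for this second estimand.

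Section 5.11.1 then plans a missing-not-at-random sensitivity analysis "for the primary analysis for both efficacy and treatment regimen estimands". It is a copy-reference pMI that "assumes that the drug effect in missing data and post-rescue data in both the placebo arm and dulaglutide arm was like the observed effect" seen on placebo; values collected after rescue are left out of that reference. The completed data go through the primary MMRM. No separate rule is given for either estimand. The section then presents the approach as a worst reasonable case for both estimands, in hedged terms ("This particular MNAR assumption can be viewed as a").

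A tipping-point analysis follows: "For both the efficacy estimand and the treatment regimen estimand, a tipping point analysis will be performed in which the missing data are imputed" under missing at random, with a shift added in the dulaglutide arm.

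**The concern.** Post-rescue values count as missing under the efficacy estimand, so the pMI text fits there. Under the treatment-regimen estimand a collected post-rescue value is an observed outcome, and the missing-at-random assumption says nothing about it. Replacing it changes the quantity estimated.

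As written, one rule yields one imputed analysis that serves both estimands. For the treatment-regimen estimand it does two things at once:

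- It imputes truly missing dulaglutide values as placebo-like, which shrinks the difference.
- It removes the effect of rescue from both arms, which widens the difference if rescue is commoner on placebo.

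The net direction is not fixed. At stake is the reading of the only reference-based sensitivity result for the estimand the regulator requested: it could be presented as a worst reasonable case while being more favourable than the result it is meant to stress.

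**Working it through.** **Inputs from the SAP (section 5.1):** difference 0.55, SD 1.2, two-sided level 0.025, 90% power, 15% dropout. These reproduce the plan's figures:

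- n = 2 × (1.2/0.55)² × (2.241 + 1.282)² = 118.2, so 119 per arm against 120 stated (power at 120 is 90.5%).
- 120/0.85 gives 142; 142 × 3 = 426; 426/0.60 = 710.
- Standard error of the difference = 1.2 × √(2/120) = 0.155.

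None of these depends on the pMI. The SAP gives no rescue rate or rescue effect, so those below are assumptions.

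**The text side by side**

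| Estimand | Post-rescue values in the primary analysis | Post-rescue values in the pMI |
|---|---|---|
| Efficacy | not used | replaced (consistent) |
| Treatment regimen | used | replaced (inconsistent) |

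**Closed form, rescue the only event.** Let r0 and r1 be the rescued shares on placebo and dulaglutide, and g the HbA1c gain from rescue. Unrescued, rescued patients would sit at h on placebo and h − 0.55 on dulaglutide. With rescue they are observed at h − g and h − 0.55 − g. The pMI puts both at h. Then

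pMI difference − treatment-regimen difference = r1(0.55 + g) − r0·g.

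A negative value means the pMI is more favourable to dulaglutide.

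- r0 = 5%, r1 = 1%, g = 1.0: 0.0155 − 0.05 = −0.0345.
- r0 = 10%, r1 = 3%, g = 1.0: 0.0465 − 0.10 = −0.0535.
- r0 = r1 = 5%, any g: 0.05 × 0.55 = +0.0275 (conservative).
- g = 0: r1 × 0.55, never negative (conservative whenever any dulaglutide patient is rescued).

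This form lets an imputed dulaglutide patient keep no drug benefit. Copy reference keeps some through earlier visits, so simulation is the better guide to size.

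**Simulation A** (1,000,000 per arm; three visits; correlation 0.6; rescue triggered by a high second-visit value; 15% missing at random). Aligned means that post-rescue values are kept and only missing values are imputed.

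| Rescue placebo/dulaglutide | Gain | Primary | pMI as written | Aligned pMI |
|---|---|---|---|---|
| 1.8%/0.6% | 1.0 | −0.537 | −0.510 | −0.498 |
| 10.5%/4.8% | 0 | −0.547 | −0.500 | −0.510 |
| 10.6%/4.8% | 1.0 | −0.492 | −0.502 | −0.452 |
| 10.6%/4.8% | 1.5 | −0.462 | −0.502 | −0.420 |
| 20.2%/10.6% | 1.5 | −0.404 | −0.488 | −0.362 |

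In the three rows with about 10.5% rescue on placebo, the primary moves from −0.547 to −0.462 as rescue works better, while the pMI as written stays at −0.50. It cannot respond to data it discards. At the extreme, with no dropout, rescue 20.2%/10.5% and gain 1.5, the primary was −0.408 and the pMI −0.527, a gap of 0.12.

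**Simulation B** (40,000 per arm; four visits; 72 scenarios: placebo rescue 2–16%, dulaglutide 1–9%, effect 0.5, 1.0 or 1.5, dropout 5, 10 or 15%, adjacent-visit correlation 0.74 or 0.87).

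- The pMI as written was more favourable than the primary in 39 (by up to 0.08), within 0.002 in 7, and less favourable in 26 (by up to 0.035).
- By rescue effect it was more favourable in 3 of 24 at 0.5, 16 of 24 at 1.0 and 20 of 24 at 1.5.
- The aligned pMI was less favourable than the primary in all 72, by 0.009–0.041.
- Rescue 15.4%/8.4%, effect 1.5, 15% dropout, correlation 0.74: primary −0.43, as written −0.49, aligned −0.39.
- Rescue 2.5%/1.0%, effect 0.5, same dropout and correlation: −0.54, −0.50, −0.50.

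**At trial size** (142 per arm, 400 trials per setting, rescue about 10%/5%, effect 1.0, 15% dropout) the pMI as written was more favourable than the primary in 44–58% of trials, and the aligned pMI in 2–3%. With rare rescue and effect 0.5 the figures were 10–16% and 2–3%.

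**The case against.** The same section already gives the treatment-regimen estimand a second departure-from-MAR check, the tipping-point analysis, which acts on missing values only and so is aligned. The pMI's handling of rescue is stated openly, the label is hedged, and both primary analyses are reported, so a reader can see what rescue handling does.

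The direction rests on rescue rates and effects absent from the SAP. The count of 39 in 72 reflects the grid chosen and is not a probability: two-thirds of it uses effects of 1.0 or 1.5, which are 1.8 to 2.7 times the planned 0.55. The gaps are small, too. In the heavier example, −0.43, −0.49 and −0.39 divided by 0.155 give about 2.8, 3.2 and 2.5, all beyond the 2.24 critical value for the 0.025 level. Finally, including post-rescue data in the placebo reference is partly a matter of preference.

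Most of this stands and limits the weight of the point. The counts show that the direction can go either way, not how likely harm is. But none of it makes a collected post-rescue value missing under this estimand, and an aligned tipping-point analysis does not correct the label on the pMI. The reference choice is not decisive: in a further 18 scenarios (400,000 per arm) the version keeping observed post-rescue values was less favourable than the primary whichever placebo reference was used for the dulaglutide imputations.

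**Conclusion.** The point holds. For the treatment-regimen estimand the pMI contradicts section 5.2. That follows from the text alone and needs no assumption. The second conclusion, that the pMI is not assured to be a worst reasonable case there, depends on rescue: it is conservative when rescue is rare, weak or balanced between arms, and more favourable than the primary when rescue is effective and clearly commoner on placebo. Under the assumed ranges the favourable gap is up to 0.08 over the 72 scenarios, about half a standard error, and 0.12 at the extreme of Simulation A. No change of conclusion was shown in the worked examples. The harm is confined to how one sensitivity result is read, but it concerns the estimand that prompted the revision, and it is cheap to correct.

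**What to change.** Split the pMI rule in section 5.11.1 by estimand.

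- **Efficacy estimand:** keep the present text.
- **Treatment-regimen estimand:** retain all observed post-rescue values in both arms, apply copy-reference imputation only to values actually missing, and fit the placebo reference to placebo data including post-rescue values.
- **Label:** limit the worst-reasonable-case description to the efficacy version, or describe each version by its own assumption. If the present version is also shown for the treatment-regimen estimand, call it supplementary.

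This matches the plan's own practice of running the testing scheme separately per estimand (section 5.3) and the HbA1c target analysis with and without post-rescue data (section 5.12.3). It costs one or two sentences and one more imputation run. The sponsor should expect a slightly less favourable treatment-regimen sensitivity estimate: the difference would be about 0.01–0.04 smaller than in the primary under the Simulation B assumptions.
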